5.0 CURRENT TRIAL

5.1 Trial Objectives and Primary Endpoints

- 1. Assess the safety and tolerability of DUR-928 in patients with AH as determined by the absence of SUSARs.
- 2. Determine the PK of DUR-928 in patients with AH.
- 3. Assess the pharmacodynamic signals of DUR-928 in patients with AH as determined by:
 - a. Biochemical: Improvement in liver biochemistry, MELD score, and the components of the MELD score individually (INR/sCr and bilirubin) at Day 7 and Day 28 and Lille score at Day 7
 - b. Biomarkers: improvement of biomarkers PPD/CCI

5.2 Trial Rationale and Design

The study will be conducted in 2 Parts using a staggered parallel design. Part A will include patients with MELD scores of 11-20, and Part B will include patients with MELD of scores 21-30.

Within each Part, the study will be conducted using a starting dose level of 30 mg with sequential dose escalation following review of safety and PK results of the prior dose level by the sponsor, the principal investigators and the medical monitor. The planned subsequent doses of DUR-928 after the starting dose are 90 mg and 150 mg.

Patients with a MELD score of 21-30 (Part B) receiving the 30 mg dose level will only be enrolled once safety review of the 30 mg dose of DUR-928 in patients with MELD score 11-20 (Part A) has been completed. The subsequent dose escalation in each Part will not proceed until the sponsor, the principal investigators, and the medical monitor complete the review of safety and evaluate PK results of the 30 mg dose level and determine it is safe to do so.

If no SUSAR is observed and PK results are satisfactory, dose escalation to the next dose cohort will proceed. All patients will be followed up to Day 28.

Figure 1: Trial Schema

5.3 **Population**

[figure not shown]
Patients with AH will be enrolled at clinical sites in the US. The target number of participants to complete the study is 24-36. During the trial, patients should receive standard of care as determined by their PI.

5.3.1 Inclusion Criteria

To participate in this study, patients must meet all of the following criteria:

- 1. Able to provide written informed consent (either from patient or patient's legally acceptable representative)
- 2. Male or female patients 21 years of age or older with BMI \geq 20 to \leq 40 kg/m²
- 3. Patients with alcoholic hepatitis defined as:
 - a. History of heavy alcohol abuse: > 40 g/day in females or > 60 g/day in males for a minimum period of 6 months, AND
 - b. Consumed alcohol within 12 weeks of entry into the study, AND
 - c. Serum bilirubin > 3 mg/dL AND AST > ALT, but less than 300 U/L AND
 - d. MELD score between 11-30, inclusive

4. No evidence of active infection as determined by the investigator.

- 5. Women of child-bearing potential (defined as females who are not surgically sterile or who are not over the age of 52 and amenorrheic for at least 12 months) must utilize appropriate birth control throughout the study duration.
- Male patients must agree to use a medically acceptable method of contraception/birth control throughout the study duration.

[figure not shown]
5.3.2 Exclusion Criteria

The patient will be excluded if one of the following criteria is met:

- 1. Other or concomitant cause(s) of liver disease as a result of:
 - a. Autoimmune liver disease PPD/CCI
 - b. Wilson disease PPD/CCI
 - c. Vascular liver disease
 - d. Drug induced liver disease

- 2. Co-infection with human immunodeficiency virus (HIV)
- 3. Positive Urine Drug Screen PPD/CCI

- 5. Active tuberculosis on chest x-ray at study entry
- 6. Significant systemic or major illness other than liver disease, PPD/CCI
- 7. Patients requiring the use of vasopressors or inotropic support.
- 8. Liver biopsy, if carried out, showing findings not compatible with AH
- 9. Any patient that has received any investigational drug or device within 30 days of dosing or who is scheduled to receive another investigational drug or device at any time during the study
- 10. PPD/CCI
- 11. If female, known pregnancy, or has a positive serum pregnancy test, or is lactating/breastfeeding
- 12. Serum creatinine > 2.5 mg/dL
- 13. Patients who have had organ transplantation PPD/CCI
- 14. Stage 3 or greater encephalopathy by West Haven criteria

5.3.3 Number of Patients

Each dose cohort will have at least 4 and no more than 6 patients. There will be 3 dose cohorts in each part of the study. The total number of participants to complete the study is at least 24 and no more than 36.

5.3.4 **Dosage and Regimen**

by slow intravenous infusion over approximately 2 hrs PPD/CCI until entire dose is given. If a patient meets the hospital discharge criteria prior to the 2nd dose, the patient will receive only one dose of DUR-928 instead of 2 doses.

See Section 5.2 for details on dose escalation.

6.0 TRIAL CONDUCT

6.1 **Investigative Sites**

This will be a multicenter study with approximately 10 clinical sites in the US.

6.2 Sponsor Obligations of Trial Conduct

Sponsor responsibilities such as data management (including electronic data capture), site management, site monitoring, medical monitoring, and central laboratory services for PK and biomarkers will be transferred to one or more contract research organizations (CROs).

6.3 **Duration**

Patient participation is approximately 33 days.

6.4 **Discontinuation of Trial**

DURECT Corporation reserves the right to terminate the trial at any time.

7.0 TRIAL PROCEDURES

The study procedures are listed below PPD/CCI

7.1 **Trial Test Drug**

7.1.1 **Dosing schedule and Proposed Dose**

DUR-928 will be administered after the patient is confirmed with the clinical diagnosis of AH. A total of no more than two doses of DUR-928 will be given, with 72 hrs between each dose.

A second dose of the assigned study treatment (test drug) will be repeated 3 days after Dose 1 to patients who are still hospitalized. If a patient meets the discharge criteria prior to Day 4, the patient will receive only one dose of DUR-928.

A Cohort Management System will be used to assign patients based on their MELD score to the appropriate Part and Cohort and associated dose.

Patients of Part A (MELD 11-20) will follow the dose escalation procedure based on cohort; each patient will receive an intravenous infusion dose of:

• Cohort 1A: 30 mg of DUR-928in PPD/CCI administered over approximately 2 hrs via IV infusion.

- Cohort 2A: 90 mg of DUR-928 in administered over approximately 2 hrs via IV infusion.
- Cohort 3A: 150 mg of DUR-928 in PPD/CCI administered over approximately 2 hrs via IV infusion

Dose escalation to the next cohort will be determined after review of safety, tolerability and pharmacokinetic data of the previous cohort.

Dose escalation for Part B will follow the same requirements as for Part A. The dose levels for Part B are planned to be the same as Part A.

Patients of Part B (MELD 21-30) will follow the dose escalation procedure based on cohort; each patient will receive an intravenous infusion dose of:

- Cohort 1B: 30 mg of DUR-928 in administered over approximately 2 hrs via IV infusion.
- Cohort 2B: 90 mg of DUR-928 in administered over approximately 2 hrs via IV infusion.
- Cohort 3B: 150 mg of DUR-928 in PPD/CCI administered over approximately 2 hrs via IV infusion

More details on preparation and administration of study drug will be provided in the Investigation Product Manual for this study.

7.1.2 Packaging and Labeling of Test Drug

The sponsor will supply the sterile ready to use DUR-928 Injection, Each vial is labeled with product name, lot number, and quantity.

7.1.3 Storage of Test Drug

PPD/CCI

7.1.4 Preparation of Test Drug

The DUR-928 Injection will be diluted into a PPD/CCI intravenous solution infusion bag. The DUR-928 solution will be administered to the patient by IV infusion over approximately 2 hrs. The diluted DUR-928 in PPD/CCI

7.1.5 **Drug Accountability**

All materials supplied are for use only in this clinical study and should not be used for any other purpose.

The Investigator is responsible for investigational product accountability, reconciliation, and record maintenance at the investigational site. In accordance with all applicable regulatory requirements, the Investigator or designated site staff must maintain investigational product accountability records throughout the course of the study. This person will document the amount of investigational product received from DURECT, the amount administered to patients, and the amount of investigational product remaining.

A Drug Dispensing Log must be kept current and will contain the following information:

- Study identification of the patient to whom the drug was dispensed;
- Date(s), study treatment cohort, and quantity of the drug dispensed to each patient.

The inventory must be available for inspection by the study monitor during the study. Drug supplies will either be returned by the Investigator or designee to DURECT or, if requested in writing by the Sponsor, unused drug supplies may be destroyed by the clinical study unit according to local standard operating procedures (SOPs). Records shall be maintained by the Investigator of any such alternate disposal of the test drug. These records must show the identification and quantity of each unit disposed of, the method of destruction (taking into account the requirements of local law), and the person who disposed of the test substance. Documentation of the disposition of all IP will be provided to DURECT. If the clinical study unit is unable to dispose of the investigational product, unused drug will be returned to DURECT.

7.2 Trial Visits and Study Procedures

7.2.1 Screening PPD/CCI

The screening visit will be performed PPD/CCI of the day of dosing. After obtaining informed consent, patients will be assigned a patient number and screening procedures will be performed. For the patient number, patients will be numbered consecutively within each site in order of their consent into the trial. Only their assigned patient number and date of birth will identify patients to the Sponsor in order to maintain anonymity.

Screening procedures include completion of:

- Enter patient into Cohort Management System
- Review of inclusion / exclusion criteria
- Demographic information
- Medical and surgical history (including MELD score at time of AH diagnosis, if available)
- Physical examination (including weight)
- Vital signs (BP, HR, respiratory rate, temperature)
- Safety laboratory tests (clinical chemistry, hematology, urinalysis, coagulation), including MELD and Lille score parameters
- Serum pregnancy test (females of childbearing potential)
- Hepatitis B, C and HIV 1/HIV 2 tests

- 12-lead ECG
- Urine Drug Screen
- · PEth test

- Calculation of Maddrey Score
- Assessment of MELD
- Record prior and concomitant medications PPD/CCI
- Biomarker sample collection PPD/CCI

7.2.2 Day 1

The following procedures will be performed pre-dose unless otherwise noted:

- Review of inclusion / exclusion criteria to confirm eligibility
- Update patient status in Cohort Management System
- Vital signs (BP, HR, respiratory rate, temperature) (pre-dose and post-dose completion/end of infusion)
- Safety labs (clinical chemistry, hematology, urinalysis, coagulation)

 PPD/CCI

- 12-lead ECG (post-dose completion/end of infusion)
- Physical Exam (including weight)
- Concomitant medications
- Adverse events
- Assessment of the patient's alcohol consumption status
- Assessment of MELD
- Pharmacokinetic sample collection PPD/CCI
- Biomarkers sample collection
- Study Drug Dosing

7.2.3 **Day 2**

- Vital signs (BP, HR, respiratory rate, temperature)
- Safety labs (clinical chemistry, hematology, urinalysis, coagulation), including MELD and Lille score parameters,
- 12-lead ECG
- Physical Exam (including weight).
- Concomitant medications
- Adverse events
- Assessment of the patient's alcohol consumption status
- Pharmacokinetic sample collection
- Biomarkers sample collection

7.2.4 **Day 3**

Patients will not be kept in the hospital longer than is medically required. If patients remain hospitalized on Day 3 (48 hrs after initiation of dosing), the following procedures will be performed. Regardless of hospitalization, occurrence of AEs, intake of concomitant medications and confirmation of patient's alcohol consumption status will be assessed (in person or via phone contact):

• Vital signs (BP, HR, respiratory rate, temperature)

- Safety labs (clinical chemistry, hematology, urinalysis, coagulation),
- 12-lead ECG
- Physical Exam (including weight)
- · Assessment of the patient's alcohol consumption status
- Biomarkers sample collection
- Pharmacokinetic sample collection PPD/CCI
- Concomitant medications
- Adverse events

7.2.5 Day 4, if performed (pre-dose unless otherwise noted)

Patients will not be kept in the hospital longer than is medically required. If patients remain hospitalized on Day 4, the following procedures will be performed. Regardless of hospitalization, occurrence of AEs, intake of concomitant medications and patient's alcohol consumption status will be assessed (in person or via phone contact):

- Vital signs (BP, HR, respiratory rate, temperature)
- Safety Labs (clinical chemistry, hematology, urinalysis, coagulation), PPD/CCI
- 12-lead ECG (post-dose completion/end of infusion)
- Physical Exam (including weight)
- Concomitant medications
- Adverse events
- Assessment of the patient's alcohol consumption status
- Biomarkers sample collection
 PPD/CCI
- Study drug dosing (dose 2 of assigned study drug)

7.2.6 Day 5 and Day 6 (if performed)

Patients will not be kept in the hospital longer than is medically required. If patients remain hospitalized on Day 5 and Day 6, the following procedures will be performed. Regardless of hospitalization, occurrence of AEs, intake of concomitant medications and patient's alcohol consumption status will be assessed (in person or via phone contact):

• Vital signs (BP, HR, respiratory rate, temperature)

• Safety labs (clinical chemistry, hematology, urinalysis, coagulation), PPD/CCI

- 12-lead ECG
- Physical Exam (including weight)
- · Assessment of the patient's alcohol consumption status
- Biomarkers sample collection

- Concomitant medications
- Adverse events

7.2.7 **Day 7 (+/- 1 day)**

The following procedures will be performed via clinic visit on Day 7, or in the hospital if the patient is not discharged. Day 7 and Day 6 visits should not occur on the same day. If a subject is going to be discharged from the hospital on Day 6, then Day 6 visit should **not** be completed and Day 7 visit should be completed per visit window.

- Vital signs (BP, HR, respiratory rate, temperature)
- Safety labs (clinical chemistry, hematology, urinalysis, coagulation)
- 12-lead ECG
- Physical Exam (including weight)
- · Concomitant medications
- · Adverse events
- Assessment of the patient's alcohol consumption status
- Assessment of MELD Score
- Assessment of Lille Score
- Biomarker sample collection PPD/CCI
- UDS and PEth test

7.2.8 Day 28 (+/- 1 day) Trial Completion / Early Termination

The following procedures will be performed via clinic visit on Day 28, of which the latter will be considered the trial completion date:

- Serum pregnancy test
- Vital signs (BP, HR, respiratory rate, temperature)

- Safety labs (clinical chemistry, hematology, urinalysis, coagulation)
- 12-lead ECG
- Physical Exam (including weight)
- Concomitant medications
- Adverse events
- Assessment of the patient's alcohol consumption status
- Assessment of MELD Score
- Biomarker sample collection PPD/CCI
- UDS and PEth test

7.3 Concomitant Medication(s)

Any required treatment deemed necessary for treatment of the patient will be under the treating physician's discretion and given as medically required. All concomitant medications will be recorded on the appropriate eCRF.

7.3.1 Prohibited Concomitant Medications

Other investigational agents are the only other prohibited medication within this trial.

8.0 ASSESSMENT OF EFFICACY

8.1 Efficacy Assessments

Change in MELD score and the components of the MELD score individually (INR/sCr and bilirubin), Lille score, biochemistry and biomarkers.

8.2 Method and Timing of Assessments

MELD score will be calculated on screening, Day 1 (pre-dose), Day 7 and Day 28.

Lille score will be calculated on Day 7

Biochemistry and all safety lab parameters will be collected at PPD/CCI

9.0 ASSESSMENT OF SAFETY

9.1 Safety Assessments

Safety will be determined based on clinical and laboratory monitoring.

Clinical: At each study follow-up visit, patients will have a physical examination with specific attention to pulmonary abnormalities, worsening in liver function as noted by increasing jaundice, ascites, or hepatic encephalopathy and presence of infection.

Laboratory: Biochemical parameters that are monitored include CRP, liver biochemistry, creatinine, and electrolytes.

Stopping Criteria:

The study will also be halted for adjudication review if more than 2 patients have an adverse event grade 3 or above on the CTCAE scale that is determined to be possibly or probably attributable to study drug as per the Adjudication Committee.

PPD/CCI

The Adjudication Committee will also be contacted *ad hoc* when there is question of symptom causality for SUSAR's.

The following parameters will be recorded for the safety evaluation:

- Adverse events
- Standard 12-lead ECG
- Safety Laboratory Tests (clinical chemistry, hematology, coagulation, and urinalysis)
- Vital Signs and Physical Examination

9.2 Method and Timing of Assessments

Safety will be evaluated using adverse events, vital signs, clinical laboratory tests and electrocardiograms. Refer to Table 1 for the frequency of assessments.

9.2.1 Adverse Event Recording

Adverse events will be recorded from the time the patient signs the informed consent form through trial completion final visit/early termination (see Section 7.2.8).

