An unexpected serious adverse event (USAE) is any serious adverse event that is independent of the underlying liver disease causality and is not consistent with information in the current Investigator's Brochure, the protocol, and the consent document.

Adverse Reaction

An adverse reaction (AR) is any untoward and unintended response to a test drug that has been considered to have a causal relationship with the treatment.

Suspected Unexpected Serious Adverse Reaction

A suspected unexpected serious adverse reaction (SUSAR) is an adverse reaction that is serious and where the nature or severity of which is not consistent with information in the current Investigator's Brochure.

Abnormal Laboratory Value as an AE

An abnormal laboratory value (i.e. any clinical laboratory abnormality or change that suggests a disease and/or organ toxicity and is of a severity that requires active management [i.e. change of test drug dose, discontinuation of test drug, medical treatment, more frequent follow-up or diagnostic investigation]), will be regarded as an AE. If clinical sequelae have been associated with a laboratory abnormality the diagnosis or medical condition should be reported (e.g. renal failure, hematuria) to replace the laboratory abnormality (e.g. elevated creatinine, urine RBC increased).

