9.3.2 Adverse Event Reporting

All events that meet the definition of an AE that occur in the period from when the patient has signed the informed consent form (ICF) through trial completion (final visit), or early

termination, must be recorded on the adverse event eCRF. All SAEs will be recorded on the appropriate eCRF and on the Serious Adverse Event Report Form from the time written informed consent has been obtained through trial completion (final visit), or early termination.

At each contact between the investigative site and the patient (visit or phone), after the patient has had an opportunity to spontaneously mention any problems, the Investigator should inquire about the occurrence of AEs. The following are examples of open-ended questions that may be used to obtain this information:

"How are you feeling?"

"Have you had any medical problems since your last visit/assessment?"

"Have you taken any new medicines, other than those given to you in this study, since your last visit/assessment?"

All AEs and SAEs will be documented in source records at each assessment time or when otherwise volunteered by the patient and recorded on the appropriate eCRF. Information to be collected includes the nature, date and time of onset, severity, duration, relationship to test drug, and outcome of the event. Even if the Investigator assesses the AE as not reasonably attributable to the test drug, its occurrence must be recorded in the source documents and reported on the eCRF along with the assessment of association.

The Investigator will treat the patient as medically required, and this may extend beyond the duration of the trial. The Investigator will record treatment and medications required to treat AEs on the appropriate eCRF(s). All SAEs, and any possibly/probably related severe AEs will be followed until resolution (no further changes in the event are expected, i.e., the point at which a patient experiencing such an AE is appropriately treated and stabilized even though they may continue to experience lingering sequelae that may never resolve.

DURECT's designee will evaluate all AEs with respect to seriousness, causality and expectedness in accordance with Directive 2001/20/EC (3) and FDA Guidelines. The expectedness of an AE will be determined according to the current version of the Investigators Brochure.

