9.3.3 Reporting of Serious Adverse Events

Regardless of causality, the investigator must complete and submit an SAE form to within 24 hrs of

knowledge of the event for all serious adverse events.

The Investigator must indicate the SAE's relationship to test drug and sign the SAE form. When additional relevant information (final diagnosis, outcome, results of specific investigations, etc.) becomes available, the investigator must record that follow-up information in the eCRF. Follow-up information should be recorded according to the process used for reporting the initial event as described above. The investigator will follow all reportable events (i.e., SAEs) until resolution. Resolution means no further changes in the event would be expected, i.e., the point at which a patient experiencing such an AE is appropriately treated and stabilized even though they may continue to experience lingering non-serious sequelae that may never resolve.

will follow all SAEs until resolution (no further changes in the event are expected, i.e., the point at which a patient experiencing such an AE is appropriately treated and stabilized even though they may continue to experience lingering sequelae that may never resolve).

PPD/CCI will report all SAEs to DURECT within 1 business day of receipt.

All serious adverse events will also be reported on the AE CRF and concomitant medications administered in association with the serious AE will be documented on the CM CRF.

If a serious adverse event occurs and comes to the attention of the Investigator after trial completion/termination within 30 days of test drug dosing or within 30 days of the last trial visit (whichever occurs later), it must be reported immediately to PPD/CCI in the same manner as the serious adverse events occurring during the trial. Investigators are not obligated to actively seek AEs from former study participants.

The Investigator must report SAEs to the IRB/IEC (per the IRB/IEC guidelines/SOPs), including all SAEs that have occurred at the investigative site and all trial related SAEs that have resulted in an expedited safety report to a regulatory agency. Concurrently, the Investigator must send DURECT documentation of such IRB/IEC notification or if reporting is not required immediately per IRB/IEC guidelines, then a copy of the local SOP stating the reporting guidelines should be supplied by the site to DURECT and the CRO.

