14.4.1 Patient Withdrawal

Patients will be informed during the informed consent process (in writing and verbally) that they are free to withdraw from the trial at any time. The Investigator may exercise his medical judgment to terminate a patient's participation in the trial due to clinically relevant changes in any clinical or laboratory parameter.

DURECT

Corporation also reserves the right to terminate the trial at any time. All trial procedures normally performed at completion of the trial must be done at the time of the patient's early termination, before the scheduled final clinic visit, or on the scheduled final clinic visit as described in Section 7.2.7 unless the patient withdraws consent. If a patient withdraws consent they will be encouraged to complete an early termination visit and AE follow-up. Patients with ongoing SAEs and any possibly/probably related severe AEs will be followed until resolution. Resolution means no further changes in the event are expected, i.e., the point at which a patient experiencing such an AE is appropriately treated and stabilized even though they may continue to experience lingering sequelae that may never resolve. Patients with ongoing adverse events (other than SAEs, and any possibly/probably related severe AEs) will be followed until resolved or until 30 days after the patient's last trial visit, whichever comes first.

Patients who withdraw prior to assignment of test drug will be considered as screen failures. If a patient discontinues prior to completion of the 24 hour PK sample they will be replaced, since PK is one of the criteria for dose escalation assessment.

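### Adverse-event collection closes at early termination, so new events in dosed patients who have not withdrawn consent are not actively sought to Day 28

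*Combined protocol and SAP*

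**What the plan says.** **When recording stops.** Section 9.2.1: "Adverse events will be recorded from the time the patient signs the informed consent form through trial completion final visit/early termination". Section 9.3.2 gives the same end point for AEs, and for SAEs it reads "from the time written informed consent has been obtained through trial completion (final visit), or early termination".

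**How participation can end.** Under Section 14.4.1 the investigator may "terminate a patient's participation in the trial due to clinically relevant changes in any clinical or laboratory parameter". Completion procedures are due at that point.

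**What happens afterwards.** Under Sections 9.3.4 and 14.4.1, ongoing SAEs and drug-related severe AEs are followed to resolution. Section 14.4.1 follows other ongoing AEs until resolved, for at most 30 days after the last visit. Under Section 9.3.3, a new SAE that reaches the investigator's attention is reportable for 30 days after dosing or after the last visit, whichever is later. The same section adds: "Investigators are not obligated to actively seek AEs from former study participants".

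**What the design promises.** Section 5.2, like the synopsis: "All patients will be followed up to Day 28".

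**How events are used.** Safety is the primary objective (Section 11.5). The ITT set is every enrolled patient who received a dose (Section 11.4). AE incidence is tabulated as counts and percentages by dose level (synopsis, Statistical Data Analysis). The halt rule in Section 9.1 counts patients with an event of grade 3 or above that the Adjudication Committee judges possibly or probably drug-related. It does not require the event to be serious.

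**The concern.** Read together, these sections close active safety collection at early termination even when the patient has not withdrawn consent. Three consequences follow.

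- **Detection.** A non-serious event that starts after termination lies outside the recording window. If it is grade 3 or above and drug-related, it may never reach the halt rule, which acts on more than 2 such patients.
- **Selection.** The ground for termination in Section 14.4.1 is a clinical or laboratory change, so observation under that clause is cut short for a reason linked to the patient's condition.
- **Denominator.** A patient observed for a few days counts in the AE percentages like one observed for 28. Section 11.5 rules out estimating missing data, and no analysis can recover events that were never collected.

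With 4 to 6 patients per cohort, one such patient is 1/4 = 25% to 1/6 = 17% of the cohort.

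**Working it through.** **Plan's own figure.** Section 5.3.3 gives 3 cohorts in each of 2 Parts, with 4 to 6 patients each: 2 × 3 × 4 = 24 and 2 × 3 × 6 = 36. This matches the stated 24 to 36.

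**Inputs.** Planned end of follow-up is Day 28 (Section 5.2). Cohort size is 4 to 6 (Section 5.3.3). Doses are on Day 1 and, if the patient is still hospitalised, Day 4 (synopsis; Section 7.1.1). The reporting tail is 30 days (Sections 9.3.3 and 14.4.1). The termination day *d* is assumed, and the termination visit is taken as the last trial visit.

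**Formulas.**
- Days available after Day 1 = 28 − 1 = 27.
- Days of active collection lost = 28 − *d*.
- Share of a cohort's post-Day-1 person-days lost = (28 − *d*) / (27 × *n*), where 27 × 4 = 108 and 27 × 6 = 162.
- Last day on which a known new SAE is reportable = the later of (last dose day + 30) and (*d* + 30). Because *d* is never before the last dose, this equals *d* + 30. The limit for following other ongoing AEs is also *d* + 30.

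| Assumed termination day | Days lost (of 27) | Cohort of 4 | Cohort of 6 | Passive SAE window ends |
|---|---|---|---|---|
| 2 | 26 (96%) | 26/108 = 24% | 26/162 = 16% | Day 32 |
| 4 | 24 (89%) | 24/108 = 22% | 24/162 = 15% | Day 34 |
| 7 | 21 (78%) | 21/108 = 19% | 21/162 = 13% | Day 37 |

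If the dose-level tables pool Parts A and B, the denominator doubles to 8 to 12 patients and the shares halve. For Day 4 they become 24/216 = 11% and 24/324 = 7%.

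**What is and is not collected after termination, without withdrawal of consent.**

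| Type of information | Collected? |
|---|---|
| SAE or drug-related severe AE ongoing at termination | Yes, to resolution |
| Other AE ongoing at termination | Yes, until resolved, for at most 30 days after the last visit |
| New SAE | Only if it becomes known; the window runs past Day 28 |
| New non-serious AE, including grade 3 or above | No |
| Remaining scheduled laboratory tests, ECGs, vital signs and examinations | No |

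The last two rows, and the passive capture in the third, are the gap.

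**The case against.** The case on the other side is substantial and limits the point in several ways.

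- **A reader might infer that patients removed for toxicity lose their safety follow-up altogether.** The documents do not support that. The event behind the removal is followed if it is recorded as an AE and ongoing, and known SAEs, deaths included, are reportable beyond Day 28.
- **A reader might infer that leaving the trial is the only way to stop drug after an abnormal finding.** This cannot be shown. The laboratory-abnormality definition in Section 9.3.1 lists "change of test drug dose, discontinuation of test drug, medical treatment" as forms of management. Section 7.1.1 also provides a one-dose path: "If a patient meets the discharge criteria prior to Day 4, the patient will receive only one dose of DUR-928". Nothing visible removes those patients from the Day 7 and Day 28 visits. Text is redacted or missing around Sections 9.1 and 14.4.1, and patient-level stopping text may sit there.
- **A reader might infer that dose escalation is biased.** That is not established. Escalation rests on SUSARs and PK (Section 5.2), and no visible text makes the review wait for Day 28 data.
- **The Day 28 sentence in Section 5.2 can be read as a general schedule** to which early termination is an ordinary exception. That is fair, and it makes this a matter for reconciliation. But the recording window and the sentence on former participants stand as written under either reading.
- **Early termination may be rare.** With at most two doses, 72 hours apart, there is little drug left to stop after Day 4, and Section 14.4.1 is permissive. No rate is given, so the figures are per affected patient.

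**Conclusion.** The point holds in a limited form. After early termination without withdrawal of consent, new non-serious AEs and the remaining scheduled safety assessments are not collected, and new SAEs are captured only passively, while the patient keeps full weight in the ITT percentages. Sections 5.2, 9.2.1, 9.3.2, 9.3.3 and 14.4.1 do not fit together on this.

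Per affected patient, terminations assumed between Day 2 and Day 7 lose 26 to 21 days of active collection. The Day 4 example costs 15% (cohort of 6) to 22% (cohort of 4) of post-Day-1 person-days. These sizes rest on the assumed termination day and on a single such patient in a cohort. The direction, under-counting of new events, follows from the text. The overall amount cannot be estimated. The conclusion does not depend on what the redacted text says about stopping drug.

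Separately, Section 14.4.1 points to the "final clinic visit as described in Section 7.2.7 unless the patient withdraws consent". Section 7.2.7 is the Day 7 visit, whereas Section 7.2.8 covers trial completion and early termination. A reader might infer that sites would run the Day 7 list and omit the pregnancy test. That is unlikely, because the same sentence calls for the completion procedures and Section 9.2.1 cites 7.2.8. This is an editorial slip.

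**What to change.** 1. In Sections 9.2.1 and 9.3.2, end AE and SAE recording at Day 28 or withdrawal of consent, instead of at early termination.
2. In Section 14.4.1, state that every dosed patient who has not withdrawn consent remains in follow-up to Day 28, with AEs, SAEs, concomitant medication and vital status actively collected. Visits or phone contact would serve; Sections 7.2.4 to 7.2.6 already allow phone contact for AEs and concomitant medication on Days 3 to 6.
3. In Section 9.3.3, make clear that such patients are not former participants before Day 28, and align Section 5.2 with the result.
4. Correct the Section 14.4.1 cross-reference from 7.2.7 to 7.2.8.

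The cost is protocol and consent wording and a few extra contacts for the patients affected. The downside is slightly higher recorded AE counts. The change concerns data collection only; no clinical stopping rule is proposed or altered.
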